U NOVARTIS

Redacted Protocol

Oncology Clinical Development & Medical Affairs

INC424 - Ruxolitinib, Jakavi

Post Authorization Safety Study CINC424AIC01T

A Non-Interventional Long-term Safety Study of Ruxolitinib in Myelofibrosis

Protocol version identifier	01 (Clean)
Date of last version of protocol	12-Jun-2014
Eu PAS register number	ENCePP number 3296
Active substance	Ruxolitinib
Active substance Medicinal product	Ruxolitinib Jakavi
Medicinal product	Jakavi
Medicinal product Product reference	Jakavi Jakavi EMEA/H/C/2464

Joint PASS

No

Research questions and objectives	 This non-interventional, observational study will provide real-world safety data on MF patients exposed and non-exposed to ruxolitinib and therefore provide insights into disease management as well as the safety profile of ruxolitinib. This is a Post Authorization Safety Study according to the EU Volume 9a of the Rules Governing Medicinal Products in the European Union. The primary objective of this Post Authorization Safety Study is to document long-term safety of ruxolitinib in patients with myelofibrosis in a real-world setting according to the current prescribing information of the European label. The secondary objectives are to document the treatment of patients with MF including pharmacological and non-pharmacological management and To document the incidence and outcome of events of special interest including the following: bleeding events serious & opportunistic infections secondary malignancies ADRs/ SAEs after discontinuation of ruxolitinib treatment Pregnancies deaths of any cause
Countries of study	Austria, France, Germany, Italy, Netherlands, Switzerland, UK
Authors	

Property of Novartis Confidential May not be used, divulged, published or otherwise disclosed without the consent of Novartis

Marketing authorization holder(s)

Marketing	Novartis Pharma A.G.
authorization holder	[name],
	[name],
	Switzerland

MAH contact person

1 Table of contents

1	Table	of content	S	4
	List o	f tables		5
	List o	f figures		5
2	List o	f abbreviat	ions	6
3	Respo	onsible par	ties	8
4	Abstr	act		8
5	Amen	dment and	l updates	. 10
6	Miles	tones		. 12
7	Ratio	nale and ba	ackground	. 13
8	Resea	rch questio	on and objectives	. 15
9	Resea	rch metho	ds	. 16
	9.1	Study de	sign	. 16
		9.1.1	Visit schedule and assessments	. 17
		9.1.2	Discussion of study design and feasibility	. 17
	9.2	Setting		. 18
		9.2.1	Patient population	. 18
		9.2.2	Inclusion and exclusion criteria	. 18

ERNEST	European Registry for Myeloproliferative Neoplasms towards a better understanding of Epidemiology, Survival and Treatment
ESA	Erythropoiesis Stimulating Agent
ET	Essential thrombocythemia
EUMNET	European Myelofibrosis Network
FAS	Full analysis set
FPFV	First patient first visit
FDA	Food and Drug Administration
GCP	Good Clinical Practices
GPP	Good Pharmacoepidemiological Practice
Hgb	Hemoglobin
HU	Hydroxyurea
ICF	Informed consent form
ICH	International Conference on Harmonization
IEC	Independent Ethics Committee
IMS	Integrated Medical Safety
IMID	Immunomodulatory Drugs
IPSS	International Prognostic Scoring System
IPSP	Individual Patient Supply Program
IRB	Institutional Review Board
ISPE	International Society for Pharmacoepidemiology
IWG-MRT	International Working Group for Myelofibrosis Research and Treatment
JAK	Janus kinase
LPFV	Last patient first visit
LPLV	Last patient last visit
MAA	Marketing Authorization Application

List of abbreviations

MedDRA	Medical dictionary for regulatory activities
MF	Myelofibrosis
MPN	Myeloproliferative neoplasms
NIS	Non-interventional Study
PASS	Post-Authorization Safety Study
PET-MF	Post essential thrombocythemia-myelofibrosis
PI	Principal Investigator
PMF	Primary myelofibrosis
PPV-MF	Post polycythemia vera-myelofibrosis
PSUR	Periodic Safety Update Report
PRBC	Packed Red Blood Cells
PV	Polycythemia vera
QoL	Quality of life
REB	Research Ethics Board
SAE	Serious Adverse Event
SCT	Stem cell transplant
SOP	Standard Operating Procedure
SmPC	Summary of Product Characteristics
STROBE	Strengthening the Reporting of Observational Studies in Epidemiology
ULN	Upper limit of normal
UTI	Urinary tract infection
WHO	World Health Organization
WBC	White blood cell count

3 Responsible parties

4 Abstract

Title	Non Interventional Ruxolitinib in Myelofibrosis Long term Safety Study
Version and Date	Version 01
	11 April 2014
Name and affiliation of main author	
Rationale and background	Myelofibrosis, an orphan condition, is a myeloproliferative neoplasm characterized by progressive anemia, leucopenia or leucocytosis, thrombocytopenia or thrombocythemia, profound remodeling of bone marrow architecture with fibrosis, and multiorgan extramedullary hematopoiesis, which primarily involves the liver and spleen.
	Ruxolitinib is a first-in-class oral JAK 1/JAK 2 inhibitor studied for the treatment of myelofibrosis. There were two Phase III pivotal studies: COMFORT-I (Verstovsek et al. 2012), a placebo controlled study of 309 patients, randomized 1:1, conducted in the US, Canada, and Australia under FDA Special Protocol Assessment, and COMFORT-II conducted by Novartis (Harrison et al 2012), an open-label study of 219 patients, randomized 2:1 between ruxolitinib and BAT, conducted in nine European countries under CHMP Scientific Advice. The primary endpoint of these studies based on standard response criteria for spleen length in MF is the proportion of patients achieving ≥ 35% reduction in spleen volume from baseline at week 24 in COMFORT I, and at week 48 in COMFORT II, as measured by MRI or CT scan. Both Phase III studies met their primary endpoint of 35% reduction in spleen volume. Thrombocytopenia and anemia were predictable and manageable with dose modifications. Bleeding, most frequently presenting as bruising has been identified as a risk associated with ruxolitinib treatment, mainly in the context of thrombocytopenia. Other identified risks of are infections, although confounded by the immunocompromization due to the underlying condition.
	The data from the two Phase III study led to the subsequent registration of ruxolitinib with the health authorities both in the US and EU. Although the number of patients exposed in clinical studies is significant considering orphan status of MF, the experience is limited by the absence of post-marketing exposure including data on long term use, and the typical restrictions imposed by inclusion and exclusion criteria in clinical studies. Therefore it was agreed with the health authorities of the EMA to collect data from patients with myelofibrosis treated with ruxolitinib or with other treatments outside of clinical trial in normal clinical practice as a post- authorization safety study (PASS)
Research question and objectives	This non-interventional, observational study will provide real-world safety data on MF patients exposed and non-exposed to ruxolitinib and therefore provide insights into disease management as well as the safety profile of ruxolitinib. This is a Post Authorization Safety Study according to the EU Volume 9a of the Rules Governing Medicinal Products in the European Union
	Primary objective
	The primary objective of this Post Authorization Safety Study is to document long-term safety of ruxolitinib in patients with myelofibrosis in a real-world setting according to the current prescribing information of the European label.

	Secondary objectives
	To document the treatment of patients with MF including pharmacological and non-
	pharmacological management.
	To document the incidence and outcome of events of special interest including the following:
	bleeding events
	serious & opportunistic infections
	secondary malignancies
	deaths of any cause
Study design	This Post Authorization Safety Study is planned as a prospective, multi-center, multi- national non-interventional study for patients diagnosed with myelofibrosis
Population	Adult patients with a diagnosis of primary or secondary myelofibrosis
	Inclusion criteria
	Patients diagnosed with primary Myelofibrosis according to WHO criteria and secondary Myelofibrosis (Post- PV MF and Post –ET MF) according to IWG-MRT (International Working Group for Myelofibrosis Research and Treatment) criteria.
	Exclusion criteria
	Patients not providing informed consent
	Patients participating concurrently in an investigational study involving ruxolitinib or another JAK inhibitor.
	Note: patients previously treated with ruxolitinib through the Individual Patient Supply Program (IPSP) or enrolled in the Expanded Access Study CINC424A2401 (JUMP) and switched to commercial drug supply are eligible.
Variables	This study is observational in nature and does not impose a therapy protocol, diagnostic/therapeutic interventions or a visit schedule. Available data will be collected at patients' visits to their site. To maintain adequate data collection, the sites will be encouraged to provide any updated patient data at 3-monthly intervals.
Data sources	The data for this study will be retrieved from Oracle Clinical/Remote Data Capture 4.6.2 A designated Contract Research Organization (CRO) will perform the analysis following their own internal Standard Operating Procedures (SOPs) that have been reviewed and approved by Novartis.
	Sites enrolling patients in this study will record data on eCRF provided by Novartis (or designee) which will capture, check, store and analyze the data. CRO will follow their own internal SOPs that have been reviewed and approved by Novartis.
	Concomitant medications entered into the database will be coded using the World Health Organization (WHO) Drug Reference List, which employs the Anatomical Therapeutic Chemical (ATC) classification system. Medical history/current medical conditions will be coded using the Medical dictionary for regulatory activities (MedDRA) terminology.
Study size	The study is planned to recruit patients diagnosed with MF exposed and non-exposed to ruxolitinib with the objective of enrolling at least 300 patients exposed to ruxolitinib within 2
	years.
	Total number of ruxolitinib exposed MF patients: 300
	Total number MF patients non-exposed to ruxolitinib 150 (estimate)
	Number of sites: 100 (estimate)
	Number of patients per site: 3-5
Data analysi-	Location of sites: European Union
Data analysis	Demographic and other baseline characteristics including medical history and prior treatment will be summarized descriptively. The incidence of on- treatment adverse events will be summarized by system organ class and preferred term using the MedDRA dictionary. Similar summaries will also be produced for treatment-related adverse events. All ADR and SAE data will be analyzed for identified and potential risks as presented in the RMP

	Sample size calculation: With 300 patients, there is 95% probability that at least 1 patient will experience an adverse event that has a true probability of occurrence of 1%. Furthermore, 300 patients will provide enough precision to ensure the margin of error on a 95% confidence interval for estimating the rate of specific AEs of interest (herpes zoster, UTI, tuberculosis, bleeding, and intracranial hemorrhage) is less than 5%, assuming the observed rate is similar to what was observed in the prior phase III studies.
Milestones	

5 Amendment and updates

Changes to the specific sections of the protocol are shown in the track changes version of the protocol using red strikethrough for deletions, red underline for insertions, green double strikethrough for "moved from", green double underline for "moved to", light blue for inserted cells and pink for deleted cells.

Number	Date	Section of study protocol	Amendment or update	Reason
01	12-Jun-2014	Entire protocol	The content of the original version has been reported consistently with the new template structure	To adapt the original protocol to the new Novartis template for non- interventional studies
		Cover page	Author's list has been revised and new authors added	Update the author's list
		Original version: Synopsis (Objectives) Version 01: Section 4 (Research question and objectives)	The bullet points: "ADRs/SAEs" and "pregnancies" have been deleted	To correct the list of the events of special interest and make it consistent with the list reported in the protocol
		Original version: Synopsis	 The following paragraphs: Dose regimen treatment cycle supply, preparation administration special safety assessments have been deleted because not foreseen in the new template 	To adapt the original protocol to the new Novartis template for non- interventional studies
		Original version: Synopsis (key milestones)	The following date:	To update the protocol milestones according to the new timelines

[figure not shown]
Table 5-1	Study protocol amendments and updates
-----------	---------------------------------------

Number	Date	Section of study protocol	Amendment or update	Reason
		Version 01: section 4 (milestones)		
		Version 01: Section 4	Countries involved added	To adapt the original protocol to the new Novartis template for non- interventional studies
		Original version: Section3.1 Version 01: Table 6.1 and section 9.1	FPFV actual date has been inserted and the following timelines:	To update the timelines
		Original version: Section3.1 Version 01: Table 6.1 and Section 9.1	FPFV actual date inserted	To update the timelines
		Original version: synopsis and Section 3.2.1 Version 01: Section 4 and Section 9.2.2	Inclusion criterion: reference to IWG-MRT criteria for diagnosis of secondary Myelofibrosis has been inserted	To clarify the diagnostic criteria used to enroll secondary MF patients
		List of abbreviations	New terms inserted	To adapt the list to the new Novartis template for non- interventional studies
		Original version: Section 3.3.4 Version 01: Section: 9.3.4	The term "Event of special interest" has been inserted in this paragraph	To update the sentence
		Version 01: Section 9.4	The new paragraph: "data sources" has been inserted	To adapt the original protocol to the new Novartis template for non- interventional studies

Novartis	Confidential
Non-Interventional Study Amended Prot	ocol v01 (Clean)

Number	Date	Section of study protocol	Amendment or update	Reason
		Original version: Section 4.3 Version 01: Section: 9.6.3	The sentence: "the data are de-identified and moved from the database maintainer to the analysis database of the sponsor" has been corrected as follows: "the data will be moved to the analysis data set"	To clarify the data transfer procedure
		Original version: Table 5.1 Version 01: Table 9.1	UTI has been deleted and tuberculosis has been inserted	To correct the table footer
	9.8control" has been instructionOriginal version: section Figure 6-1 Version 01: Figure 12.1The sentence: "period transfer of data colle CINC424AIC01T and required in the ELN disease registry" has corrected deleting "p and inserting "cleaned		The new paragraph: "quality control" has been inserted	To adapt the original protocol to the new Novartis template for non- interventional studies
		The sentence: "periodic transfer of data collected in CINC424AIC01T and required in the ELN ERNEST disease registry" has been corrected deleting "periodic" and inserting "cleaned"	To correct the sentence on data transfer	
		Version 01: Annex 2	The ENCePP check list has been added	To adapt the original protocol to the new Novartis template for non- interventional studies

6 Milestones

7 Rationale and background

Myelofibrosis (MF) is a myeloproliferative neoplasm. The condition of interest includes all types of MF, i.e., primary myelofibrosis (PMF), and secondary myelofibrosis: postpolycythemia vera MF (PPV-MF) or post-essential thrombocythemia MF (PET-MF). The 10-year risk of developing MF is < 4% in ET and 10% in PV. The median age at diagnosis is approximately 65 years (Barbui et al. 2011). The incidence of PMF has been shown to increase with age and is estimated at 0.4 to 1.4 cases per 100,000 individuals per year in Western countries. The condition fulfills the criteria of an orphan disease.

Patients with PMF, PPV-MF, or PET-MF have a critical unmet medical need. MF patients suffer from debilitating symptoms and often massive splenomegaly (Barbui et al. 2011, Mesa et al. 2007). None of the previously available drugs used to treat MF was approved for use in this indication in the United States until the approval of ruxolitinib in November 2011. In the EU, HU is approved on a national basis in a few countries (e.g. France, Italy, Sweden and Spain) and is used to control excessive myeloproliferation. Other therapeutic options include splenectomy, splenic irradiation and the potentially curative option of allogeneic stem cell transplant (Ciurea et al. 2008; Bacigalupo et al. 2010). Splenectomy has been reported to result in perioperative complications in 31% and death in 9% of patients.

The disease is known to be associated with dysregulated JAK1 and JAK2 signaling. These mediate the signaling of a number of cytokines and growth factors that are important for hematopoiesis and immune function. The basis for the dysregulation is believed to include high levels of circulating cytokines that activate the JAK-STAT pathway, gain-of function mutations such as JAK2V617F, and silencing of negative regulatory mechanisms.

MF can present as an apparently de novo disorder (PMF) or evolve from other MPNs, and can be termed secondary MF, PPV-MF or PET-MF (Mesa et al. 2007; Barbui et al. 2011). The hallmark feature of MF is massive splenomegaly. The clinical presentation of the disease is also characterized by progressive anemia, leucopenia or leucocytosis, thrombocytopenia or thrombocythemia, profound remodeling of bone marrow architecture with fibrosis, and multiorgan extramedullary hematopoiesis, which primarily involves the liver and spleen (Mesa et al. 2007; Barbui et al. 2011). Patients may experience severe constitutional symptoms, sequelae of massive splenomegaly (portal hypertension, hepatic obstruction and splenic infarction), dyspnea, pain, limited mobility, early satiety, a catabolic state with cachexia, ineffective hematopoiesis and hematopoietic failure, risk of vascular events (including thrombosis and hemorrhage), progression to leukemia, and premature death. Causes of death for patients with MF include leukemic transformation, infections, bleeding, thrombosis, heart failure, liver failure, solid tumors, respiratory failure, and portal hypertension (Cervantes et al. 2009).

Novartis	Confidential	Page 14
Non-Interventional Study Amer	nded Protocol v01 (Clean)	Study No. CINC424AIC01T

A retrospective multicenter analysis reported by (Cervantes et al. 2009) on behalf of the International Working Group for Myelofibrosis Research and Treatment (IWG-MRT) identified 5 risk factors independently associated with shortened survival in PMF: age > 65 years, presence of constitutional symptoms (weight loss, fever, or night sweats), anemia as determined by hemoglobin (Hgb) < 10 g/dL, leukocytosis (white blood cell [WBC] count > 25 x 10⁹/L), and a circulating blast percentage of \geq 1%. This scoring system is termed the International Prognostic Scoring System (IPSS). The IWG-MRT identified 4 risk groups with non-overlapping survival curves based on the absence or presence of 1 or more of these risk factors. The median survival of patients was 135 months in the Low risk group (zero risk factors), 95 months in the Intermediate-1 risk group (1 risk factor), 48 months in the Intermediate-2 risk group (2 risk factors), and 27 months in the High risk group (\geq 3 risk factors). Analysis of relative survival showed that mortality in all of the patients at 5 and 10 years after diagnosis was 40% and 60% greater, respectively, than the expected mortality in a general population with similar demographic characteristics. Further study of the IPSS has resulted in the development of two additional scoring systems to assess the prognostic value of risk factors emerging after patients are diagnosed with PMF: the Dynamic International Prognostic Scoring System (DIPSS) which increases the relative importance of the presence of anemia in the prognostic model in proportion to its greater association with decreased survival (Passamonti et al. 2010); and the DIPSS Plus, a refined scoring system that additionally accounts for karyotype, platelet count, and transfusion status information (Verstovsek et al. 2010).

Patients with PMF, PPV-MF, or PET MF have a critical unmet medical need. Hydroxyurea as well as other therapies commonly used to treat MF (erythropoietic-stimulating agents, androgens and steroids) have been evaluated in small series of patients, and never in a randomized, controlled Phase III study. Other drugs including busulfan, melphalan, and 2chlorodeoxyadenosine have been used to treat patients refractory to HU, but have had little or no effect on the disease. Few patients treated with these agents experience broad or durable clinically meaningful improvement in their symptoms and tolerability is variable. Splenectomy has been reported to result in perioperative complications in 31% and death in 9% of patients. Although splenic irradiation has been associated with reductions in spleen size in 80-95% of cases and relief in abdominal discomfort in up to 100% of the patients for a median of six months, it is associated with significant and prolonged myelosuppression with a mortality rate as high as 13%. The only potentially curative therapy for MF remains allogeneic stem cell transplantation (alloSCT). However, not only is donor availability a limiting factor, but the 1-year transplant-related mortality in patients who undergo alloSCT is 27%, and alloSCT is rarely a viable option in patients > 60 years of age (Bacigalupo et al. 2010; Ciurea et al. 2008). In the review of the DIPSS only 8 of 525 patients (1.5%) had undergone an alloSCT, demonstrating the rarity of this therapeutic option for most MF patients. Overall, the low success rate of existing therapeutic interventions used to treat MF attests to a substantial medical need.

Novartis	Confidential	Page 15
Non-Interventional Study Ame	ended Protocol v01 (Clean)	Study No. CINC424AIC01T

There were two Phase III pivotal studies: COMFORT-I (Verstovsek et al. 2012), a placebo controlled study of 309 patients, randomized 1:1, conducted in the US, Canada, and Australia under FDA Special Protocol Assessment, and COMFORT-II conducted by Novartis (Harrison et al. 2012), an open-label study of 219 patients, randomized 2:1 between ruxolitinib and BAT, conducted in nine European countries under CHMP Scientific Advice. The primary endpoint of these studies based on standard response criteria for spleen length in MF is the proportion of patients achieving \geq 35% reduction in spleen volume from baseline at week 24 in COMFORT I, and at week 48 in COMFORT II, as measured by MRI or CT scan. This volumetric reduction corresponds with the European Myelofibrosis Network (EUMNET) and IWG-MRT definitions of Clinical Improvement. Secondary endpoints include durability of spleen response, symptomatic improvement, as well as leukemia-free survival and overall survival. Both Phase III studies met their primary endpoint of 35% reduction in spleen volume.

The analysis of survival data from both trials did demonstrate a survival advantage for patients treated with ruxolitinib in the COMFORT I-trial (Verstovsek et al. 2012). However no benefit of ruxolitinib on survival was yet observed in the COMFORT II study (Harrison et al 2012), and the authors argue that this analysis may be confounded by the high crossover rate from best available therapy of 25% and withdrawal without follow-up of another 12% of the patients.

Grade 3-4 laboratory findings of anemia and thrombocytopenia were reported with ruxolitinib at rates of 38.3% and 8.3%, respectively, compared with 20.6% and 6.8% on BAT (COMFORT-II); and with ruxolitinib at rates of 45.2% and 12.9%, respectively, compared with 19.2% and 1.3% on Placebo (COMFORT-I). Thrombocytopenia and anemia were predictable and manageable with dose modifications. Bleeding, most frequently presenting as bruising has been identified as a risk associated with ruxolitinib treatment, mainly in the context of thrombocytopenia. Other identified risks of are infections, although confounded by the immunocompromization due to the underlying condition. Areas of special interest for the collection of drug usage safety data are drug exposed pregnancies and the development of secondary malignancies.

In the US, ruxolitinib was first licensed and marketed in 2011 indicated for treatment of patients with intermediate or high-risk myelofibrosis, including primary myelofibrosis, post-polycythemia vera myelofibrosis and post-essential thrombocythemia myelofibrosis. At the time point of submission of the Marketing Authorization Application in the EU, a total of 589 MF patients were exposed to ruxolitinib phase 3 studies, which was equivalent to 622 patient years of exposure. Although the number of patients exposed in clinical studies is significant considering orphan status of MF, the experience is limited by the absence of post marketing exposure including data on long term use and the typical restrictions imposed by inclusion and exclusion criteria in clinical studies. This study will provide real-world data on MF patients exposed and non-exposed to ruxolitinib and will therefore provide insights into disease management as well as the safety profile of ruxolitinib.

8 Research question and objectives

This is a Post Authorization Safety Study according to the EU Volume 9a of the Rules Governing Medicinal Products in the European Union.

Primary objective

The primary objective of this Post Authorization Safety Study is to document long-term safety in patients with myelofibrosis prescribed ruxolitinib according to the prescribing information.

[figure not shown]
Secondary objectives

- 1. To document the treatment of patients with MF including pharmacological and nonpharmacological management.
- 2. To document the incidence and outcome of events of special interest including the following:
 - bleeding events
 - serious & opportunistic infections
 - secondary malignancies
 - ADRs/ SAEs after discontinuation of ruxolitinib treatment
 - pregnancies
 - deaths of any cause

9 Research methods

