9.1.1 Visit schedule and assessments

This study is non-interventional or observational in nature and does not impose a therapy protocol, diagnostic/therapeutic interventions or a visit schedule. Available data from routine clinical management of the patients will be collected at patients' visits to their site. To maintain adequate data collection, the sites will be encouraged to provide any updated patient data at 3-monthly intervals.

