11.1 Events of special interest

For all patients enrolled in the non-interventional study data for events of special interest will be collected. Events of special interest will be prompted at each visit. For all events of special interest the following information will be collected, where applicable:

- 1. The severity grade (CTCAE Grade 1-4), event outcome
- 2. Start and end dates of the event, unless unresolved at final examination, or no further change of the condition can be expected
- 3. Diagnostic measures and results related to the event, e.g., histopathology, microbiological laboratory results
- 4. Use of anti-infective therapies, transfusions or other medications related to the management of the event

For patients exposed to ruxolitinib until 28 days after treatment discontinuation, all events of special interest that fulfill the criteria of a SAE will be reported.

Events of special interest are:

Bleeding events

Bleeding events include all hemorrhages of any severity grade (CTCAE 1-4, events with fatal outcome):

- Minor hemorrhages, such as bruising or epistaxis
- Major bleeding events, such as intracranial or intra-abdominal hemorrhages
- Unusual bleedings reported by patients (prolonged or more severe menorrhagia, prolonged bleeding after trauma)

Serious or opportunistic infections

Serious or opportunistic infections are defined as bacterial, viral, fungal or parasitic infections that fulfill one of the following criteria:

- Requires anti-infective treatment
- Leads to significant disability or hospitalization

Secondary malignancies

• Any malignancy diagnosed after inclusion of patients in the non-interventional study will be reported including diagnosis of or progression of MF to AML.

Deaths

• All deaths including cause of death will be reported. Deaths occurring in ruxolitinib exposed patients represent a SAE

11.2 Collection and reporting of Serious Adverse Events and Adverse drug Reactions for ruxolitinib exposed patients

Adverse Drug Reactions to ruxolitinib

For the purpose of this study, an Adverse Drug Reaction (ADR) is defined as a response to ruxolitinib treatment (medical condition, clinical sign, and symptom or laboratory value) which is noxious and unintended. Response in this context means that:

- A causal relationship between ruxolitinib treatment and the event is at least possible as determined by the reporter
- The event occurred after first exposure to ruxolitinib (treatment emergent)

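### All deaths are to be reported, but no vital-status check is specified once a patient stops attending

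*Protocol*

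**What the plan says.** Section 8 of the protocol lists "deaths of any cause" among the events of special interest whose incidence and outcome are a secondary objective. Section 11.1 makes this a duty in both cohorts: "For all patients enrolled in the non-interventional study data for events of special interest will be collected", and, for deaths, "All deaths including cause of death will be reported".

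The means of collection are in section 9.1.1: "Available data from routine clinical management of the patients will be collected at patients' visits to their site". No visit schedule is imposed. The same section and the Abstract add: "To maintain adequate data collection, the sites will be encouraged to provide any updated patient data at 3-monthly intervals". Section 11.1 states when events are asked about: "Events of special interest will be prompted at each visit". Section 11.2 adds that they may also come to light between visits, for example when the patient volunteers them.

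Section 9.3.5 gives four reasons for leaving the study: withdrawn consent, lost to follow-up, administrative problems and death. Section 9.4 asks that the reason for premature discontinuation be established, without saying how. The main stated measure against loss is site selection (section 9.1.2): centres should ideally have the other relevant disciplines in the same institution. Planned follow-up is 3 to 5 years.

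**The concern.** A promise to report every death needs a way to learn of deaths in patients who no longer come. The protocol describes none: no periodic status check, no query to the treating physician, no status check at study close.

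This matters over the planned horizon. Section 7 quotes median survival of 48 months in the Intermediate-2 group and 27 months in the High-risk group, so in those groups a large share of patients would be expected to die within 3 to 5 years. The protocol also knows the problem from elsewhere. In describing the open-label phase III study, section 7 reports the argument that its survival analysis may be confounded by crossover and by "withdrawal without follow-up of another 12% of the patients".

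At stake is the credibility of a stated objective. If deaths after loss go unrecorded, crude death proportions are too low. Vital status that was never collected cannot be recovered by any later analysis rule.

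**Working it through.** **Step 1: trace the routes by which a death can reach the database.**

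- The patient attends: events are prompted at the visit (11.1).
- The patient is alive between visits: events may be volunteered (11.2). A patient cannot volunteer his or her own death.
- The patient dies and the site learns of it: the death must be reported (11.1), and death is its own reason for leaving (9.3.5).
- The patient has stopped attending, then dies, and the site is not told: no route applies. The 24-hour SAE report for exposed patients starts when the event becomes known (11.2), so it does not find this death either.

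The gap is the fourth case.

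**Step 2: the plan's own figure.** Section 9.7.7 states a 95% probability of at least one event among 300 exposed patients at a true rate of 1%. Check: 1 - 0.99^300 = 0.951, which agrees. The section gives no expected number of deaths and no allowance for loss to follow-up, so the size of the gap can only be illustrated.

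**Step 3: illustration.** From the documents: medians of 135, 95, 48 and 27 months (section 7), follow-up of 3 or 5 years (9.1.2), and 300 exposed and 150 non-exposed patients (9.7.7). Assumed: exponential survival, a constant loss rate g of 0.02, 0.05 or 0.10 per year, the same mortality before and after loss, and no death after loss ever learned of.

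With λ = ln 2 / median in years:

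- deaths seen = λ/(λ+g) × (1 - e^(-(λ+g)T))
- true deaths = 1 - e^(-λT)
- share missed = 1 - seen/true

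Worked case: median 48 months, T = 5, g = 0.05. Then λ = 0.1733 and λ+g = 0.2233. Seen = 0.776 × 0.6725 = 0.522. True = 0.580. The share missed is 9.9%, or about 17 deaths per 300 patients and 9 per 150.

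Share of deaths missed (%):

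| Median (months) | Years | g = 0.02 | g = 0.05 | g = 0.10 |
|---|---|---|---|---|
| 135 | 3 | 2.9 | 6.9 | 13.2 |
| 95 | 3 | 2.8 | 6.8 | 13.0 |
| 48 | 3 | 2.7 | 6.5 | 12.5 |
| 27 | 3 | 2.5 | 6.1 | 11.6 |
| 135 | 5 | 4.6 | 11.0 | 20.3 |
| 95 | 5 | 4.5 | 10.7 | 19.9 |
| 48 | 5 | 4.2 | 9.9 | 18.5 |
| 27 | 5 | 3.7 | 8.8 | 16.4 |

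The share depends mainly on the assumed loss rate and the length of follow-up, and little on the risk group.

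**Step 4: proportions against rates.** In the worked case, observed person-time per patient is 0.6725/0.2233 = 3.01 years, and 0.522/3.01 = 0.173, which is the true λ. So if loss is unrelated to prognosis, a death rate censored at loss is unbiased and only the crude proportion is too low. If the death rate doubles after loss (assumed), deaths seen stay at 0.522 while true deaths rise to 0.611, so 14.6% are missed. The observed rate stays at 0.173 although lost patients die at twice that, so the rate is now too low as well. Across all four medians, doubling gives 4-22% missed at 3 years and 5-32% at 5 years.

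**The case against.** The protocol is not silent on completeness. Section 9.3.1 asks for every effort to record available safety data, section 11.2 foresees detection between visits, section 9.1.2 selects sites with loss to follow-up in mind, and section 9.4 wants the reason for leaving established. Completion guidelines and the monitoring plan are not shown and may ask for more. All this stands and should reduce the loss. None of it says how vital status is obtained for someone who has gone.

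Three stronger readings are tempting, and the documents do not support them.

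- **Deaths are filed as lost to follow-up.** Nothing says so. Death is a separate category, and a death the site knows of must be reported. The problem is deaths the site never hears of.
- **The under-count differs by cohort, because exposed patients also have 24-hour SAE reporting until 28 days after stopping.** That route speeds the report of a known death; it does not discover one. The duty to report all deaths covers both cohorts, and no loss rate is given for either. Section 9.1.2 also rules out direct comparison of the cohorts.
- **Patients who have died are counted as event-free.** That would need a denominator or censoring rule which the protocol does not fix and which commonly sits in the SAP.

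The 12% in section 7 is no substitute for a loss rate here: it comes from a randomised trial with crossover. It is not used above.

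A last objection is that active follow-up might sit badly with a non-interventional study. Section 9.3.1 bars examinations done only for the protocol, and a status entry from records is not one. Section 11.2 already has pregnancies followed quarterly to outcome in exposed and unexposed patients.

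**Conclusion.** The point holds as a gap in data collection: the protocol promises all deaths with cause for every enrolled patient, yet specifies no vital-status ascertainment after attendance stops. Following it as written can miss deaths over 3 to 5 years. The direction for crude death proportions is downward; for rates it is downward only if sicker patients are the ones lost.

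The illustrative range of 2.5-13% of deaths missed at 3 years and 4-20% at 5 years rests on an assumed loss of 2-10% per year, exponential survival, unchanged mortality after loss and no tracing at all. The medians come from a retrospective series in primary myelofibrosis, so the absolute counts are only indicative. Whether the cohorts would differ, and in which direction, cannot be determined from the protocol. The remedy is cheap and has to be in place while data are being collected, so it is worth making.

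**What to change.** In sections 9.1.1, 9.3.5 and 11.1, have the site record, for every enrolled patient who has not withdrawn consent, vital status, the date last known alive and, if the patient has died, the date and cause of death. Take this from site records or the treating physician, whether or not the patient has visited. Do it at each annual data cut (section 9.7.6 already plans annual summaries) and at study close, by the same rule for exposed and non-exposed patients. Report the number with unknown vital status by cohort alongside the deaths.

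The cost is one short eCRF page per patient per year, a sentence in the consent text and a little site time. No visit or examination is added, so the study stays non-interventional.
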